4.4 Interim Analyses and Data Monitoring

One formal interim analysis is planned when 2/3 of the required total number of primary efficacy endpoint events have been observed.

If the interim analysis shows clear and consistent benefit in the finerenone treatment group, the DMC may recommend early study termination. The Haybittle-Peto rule will be used to guide the decision regarding early stopping of the study for success: a reduction of 3 standard deviations in the analysis of the primary and the key secondary efficacy endpoint at the interim analysis (two-sided p-value <0.00270).

For a detailed description of the testing procedure, including an adjustment of the significance level for the interim analysis, please see section 4.7.

In case of an early stop of the study for success, the final analysis reported in the CSR will consider all events up to the subjects' respective EoS visits as would have been the case if the study had not stopped early. A sensitivity analysis will take all events up to the interim analysis datacut date into consideration and will be based on the same final clean database as done for the final analysis reported in the CSR (instead of the interim analysis database). For this sensitivity analysis, censoring dates after the datacut date will be reset to the datacut date.

For a lack of efficacy, a non-binding futility approach will be utilized at the time of the planned interim analysis. If the conditional probability of rejecting the null hypothesis for the primary comparison, given the assumed and current event rates, falls to an unacceptably low level (as specified in the DMC Charter), the DMC may consider recommending early termination of the study.

A detailed plan for the routine DMC safety analyses and the interim analysis is covered in the DMC charter, the analysis planned to be provided to the DMC is described in a separate DMC SAP with Tables, Listings and Figures (TLFs) attached to the DMC charter. The DMC will review the data in an unblinded manner, both for the routine safety tables and the interim analysis. There are no predefined stopping conditions for the ongoing safety monitoring of this trial. The statistical analysis for the DMC meetings will be performed by an independent statistical analysis center.

4.5 Data Rules

General data rules are described in this section, further data rules for specific parameters or analyses are specified in the respective subsections of section 6.

4.5.1 Baseline values

Baseline values will be defined as the last non-missing measurement before or on the day of randomization. If the last observation available prior to randomization is the measurement from the Screening Visit, this would be used as the baseline value. This also includes assessments from a local laboratory, in case that prior to randomization, no assessment from the central laboratory is available. Otherwise baseline will be missing. The measurement from the Run-in Visit will not be used as a baseline value unless otherwise specified.

If more than one measurement was planned for a scheduled visit, for example blood pressure measurements and heart rate, the mean value of these measurements per time point prior to randomization will be used as the baseline value.

4.5.2 Change from baseline

Change from baseline will in general be displayed as absolute change from baseline defined as the difference to baseline, i.e.:

$$\text{Absolute change} = \text{Post baseline value} - \text{baseline value.}$$

Some parameters will be additionally analyzed as relative change defined as

$$\text{Relative change} = 100 * [(\text{post baseline value} - \text{baseline value}) / \text{baseline value}].$$

For specific analyses, the relative decrease of a variable will be analyzed instead of the relative change. The relative decrease is equivalent to the negative of the relative change and defined as

$$\text{Relative decrease} = 100 * [(\text{baseline value} - \text{post baseline value}) / \text{baseline value}].$$

4.5.3 Other data handling

Only the data provided by the central laboratory will be used for analysis, values from local laboratories will not be used in the statistical analysis and will be listed only unless there are no values from the central laboratory available for baseline.

In case of retests for Run-in and Screening visits, the closest measurement prior to randomization will be used for analysis instead of the scheduled measurements. At all visits starting at Visit 1 and if not stated otherwise, only the values at scheduled measurements will be used for analysis. In the unexpected case that more values than planned are available for a scheduled visit, only the first valid value will be used.

For the derived visit “Any time post-baseline” (applicable for efficacy) this will include any measurement after date of randomization, including unscheduled assessments. For the derived visit “Any treatment-emergent” (applicable for safety), only assessments on or after study medication start date until 3 days after the date of any temporary or permanent interruption of study drug, including unscheduled assessments, will be considered.

For those laboratory values which are <LLOQ (Lower limit of quantification), half the value of the LLOQ will be used for analysis. Differences between 2 values <LLOQ will be assigned values of 0. Ratios between 2 values <LLOQ will be assigned a value of 1. For values which are >ULOQ (Upper limit of quantification), the ULOQ will be used for analysis. This rule does not apply to the finerenone plasma concentration data.

In case of log-normally distributed data, descriptive statistics other than minimum, maximum and median will only be calculated if at least 2/3 of the individual data were measured and were above the lower limit of quantification. In tables showing descriptive statistics, where values below LLOQ are included, these descriptive statistics will be marked.

Urinalysis is assessed 3 times per visit. UACR will be determined 3 times at each visit from first morning void urine samples collected on 3 consecutive days. For the analyses of UACR, the 3 measurements at one visit will be combined provided that at least 2 measurements are available. First, the coefficient of variation (CV) will be calculated for the 3 values as follows considering the log-normal distribution for UACR [7]:

$$CV = \sqrt{\exp(SD_{ln}^2) - 1},$$

where SD_{ln} is the standard deviation of the 3 log-transformed UACR values. If the coefficient of variation exceeds 25%, the median from the measurements will be used for the analyses. The median in case of an even number of values will be defined as the geometric mean from the 2 middle values. If the coefficient of variation is 25% at the most, the geometric mean will be used. If 2 or 3 scheduled assessments are missing or invalid and unscheduled assessments have been performed, then the set of unscheduled measurements closest to the planned visit will be used to determine the UACR at the respective visit if performed within 30 days before or after the planned time point for all visits from Visit 3 (Month 4) onwards (with the following exception: only samples with 2/3 of values no later than 30 days (for “last on-treatment” analysis) or 3 days (for “last treatment-emergent” analysis) after last study drug intake will be considered). For Visit 1, 2 out of 3 samples have to be on or before the day of randomization and have to lead to non-missing values in order for the set of samples to be valid for baseline calculation; otherwise (also including the case when there is one valid sample at Visit 1), the set of screening samples will be considered for baseline.

In the case of ESRD, the UACR and eGFR values after the onset date of ESRD will be excluded from all efficacy analyses, but included in the safety analyses.

For the stratification group type of albuminuria at screening (high or very high), the classification supplied from the central lab via IxRS will be used. The rule that has been applied by the central lab for this classification is, if there are 3 values, the median value should be taken; if 2 values, then the arithmetic mean value, regardless of degree of variation between the values. The lab reports from the run-in and screening visits will include the type of albuminuria, to assist the investigators in reducing stratification and randomization errors.

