Study drug administration			X		X						
KDQOL-36, EQ-5D-5L			X				X		X	X	
Physical examination	X	X					X		X	X	
Weight, height, waist and hip circumference ^a	X	X	X	X	X	X	X	X	X	X	
Vital signs ^b	X	X	X	X	X	X	X	X	X	X	
12-lead ECG (local)	X	X	X				X		X	X	
PK blood sample					X ⁿ		X ^o				
Full central laboratory	X	X	X		X	X	X		X	X	
Limited chemistry (central)				X				X			
Urinalysis (central) ^c	X	X	X		X		X			X	
Safety laboratory (local) ^d			X	X	X	X	X	X			
Endpoint assessment ^e				X	X	X	X	X	X	X	
AE assessment ^f	X	X	X	X	X	X	X	X	X	X	X
Pregnancy test ^g		X					X				

Table 9–1 Study 16244: schedule of activities and evaluations - amended**NOTE:**

One month corresponds to 30 days

A time frame of ± 7 days is allowed for Visit 2 (Month 1), and for the Up-titration Visit(s).

A time frame of ± 12 days is allowed for all regular visits from Visit 3 (Month 4) onwards.

Abbreviations: ECG = electrocardiogram; EOS = end of study; EQ-5D-5L = EuroQol Group 5 dimension, 5 level questionnaire; KDQOL = Kidney Disease Quality of Life; PD = premature discontinuation; PT = post-treatment; (S)AE = (serious) adverse event; SD = study drug

- ^a Height, waist and hip circumference to be assessed at Run-in Visit only.
- ^b After resting for at least 5 minutes, 3 measurements to be taken with at least 1-minute interval in a sitting position (all 3 readings within a maximum of 20 minutes).
- ^c At Visit 1, first morning void urine samples to be preferably collected on three consecutive days at the subject's home within 7 days before scheduled visit and before any intake of study drug. At the other visits the 3 consecutive samples can be collected ± 7 days from the visit date.
- ^d Blood samples (for potassium and creatinine) for measurement in the local laboratory may be obtained up to 72 hours before a scheduled visit. Samples to be taken only if the subject is still taking study drug,
- ^e Categorical renal endpoints, $\geq 40\%$ or $\geq 57\%$ decrease in eGFR compared to baseline and an eGFR decrease to less than 15 mL/min/1.73 m², have to be confirmed by at least one additional standardized serum creatinine measurement. This confirmation should be done at least 4 weeks after the initial measurement as an unscheduled assessment.
- ^f AEs related to study procedures occurring after signing the informed consent as well as all other AEs starting after randomization will be documented on the respective eCRF pages.

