9.7 Other procedures and variables

9.7.1 Monitoring of potassium - *amended*

This section was changed in Amendment 3, see Section 15.1.2.31.

Hyperkalemia is a frequent event in subjects with DKD progressing to ESRD and one of the main risks identified from previous studies with MRAs including finerenone. Potassium will be monitored closely during this study, with assessments of potassium concentration scheduled at all visits (see [Table 9–1](#) for schedule).

During treatment with study drug, all assessments of potassium, including re-tests, will be performed at both local and central laboratories. Due to sample handling and extended transportation time to the central laboratory, falsely elevated serum potassium values in centrally (but not locally) analyzed samples have been observed in previous studies with finerenone. Since the value of potassium in the local sample is usually not affected by this and results from the local laboratory are available earlier, local samples will be taken not only for safety purposes but also for dose adjustments.

Re-checking of potassium values must be done at the latest within 72 hours of the investigator being aware of results that need confirmation. The investigator can perform a re-test at any time if they consider it necessary to confirm the potassium concentration of the local or the central sample.

Adjustment of dose after start of study drug intake based on blood potassium levels is provided in [Table 9–3](#).

Table 9–3 Blood potassium: guidance for dose adjustment at Visit 2 and subsequent visits

Blood potassium (mmol/L)	Action
First sample:	
≤4.8	If on lower dose of study drug, up-titrate to higher dose. If on higher dose of study drug, continue on the same dose.
4.9 to 5.5	Continue on the same dose.
>5.5	Withhold study drug and re-check potassium within 72 hours.
Second and subsequent samples:	
≤5.0	Re-start study drug at lower dose.
>5.0	Continue to withhold study drug; continue to monitor potassium and restart study drug at the lower dose only if potassium is ≤5.0

NOTE: lower dose = 10 mg once daily; higher dose = 20 mg once daily.

The following aspects have also to be taken into consideration:

- Blood potassium should be measured 4 weeks (\pm 7 days) after re-starting treatment or dose adjustment, especially after up-titration

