9.7.2 Laboratory assessments

9.7.2.1 Central laboratory

The name and the address for the central laboratory service provider can be found in the documentation supplied by the vendor. Only centrally analyzed blood samples will be considered for statistical analysis, unless otherwise specified. Details of the collections, shipment of samples and reporting of results by the central laboratory will be provided to the investigators in the Laboratory Manual.

Laboratory evaluations (*hematology, HbA_{1c}, clinical chemistry and urinalysis* parameters) are shown in [Table 9–4](#). Hematology, HbA_{1c} and (full) clinical chemistry are considered as ‘*Full central laboratory*’ assessments.

Laboratory evaluations will be performed according to the visit schedule (see [Table 9–1](#)).

Table 9–4 Central laboratory parameters

Parameter	Component
Hematology	White blood cell count (WBC), red blood cell count (RBC), hemoglobin, hematocrit, mean corpuscular volume (MCV), mean corpuscular hemoglobin (MCH), MCH concentration (MCHC), platelets
Glycated hemoglobin (HbA1c)	HbA1c only
Clinical chemistry (full)	Aspartate aminotransferase (AST), alanine aminotransferase (ALT), alkaline phosphatase (AP), gamma glutamyl transpeptidase (GGT), lactate dehydrogenase (LDH), creatine kinase (CK), cholesterol (high density lipoprotein [HDL], low density lipoprotein [LDL], total), triglycerides, creatinine, eGFR (CKD-EPI), blood urea nitrogen, uric acid, bilirubin, sodium, serum potassium, magnesium, total protein, albumin, high-sensitivity C-reactive protein (hs-CRP)
Clinical chemistry (limited)	Serum creatinine, eGFR (CKD-EPI), sodium, serum potassium
Urinalysis	Urine albumin-to-creatinine ratio (UACR) will be measured in the first morning void urine samples collected at the subject's home on 3 consecutive days

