10.1 General considerations

Statistical analysis will be performed using SAS; the version used will be specified in the statistical analysis plan (SAP).

A log-normal distribution is assumed for serum creatinine and UACR. For all other metric variables, a normal distribution is assumed. The distributional assumptions will be investigated and if necessary, nonparametric methods or transformation of the data will be considered.

All variables will be analyzed by descriptive statistical methods. The number of data available, mean, standard deviation (SDv), minimum, median, and maximum will be calculated for metric data. The geometric mean and SDv will be provided instead of the arithmetic mean and SDv for the variables where lognormal distributions are assumed. Frequency tables will be generated for categorical data.

Baseline values will be defined as the last non-missing measurement before randomization (Visit 1). If the last observation available prior to randomization is the measurement from the Screening Visit, this would be used as the baseline value. This also includes assessments from a local laboratory, in case that prior to randomization, no assessment from the central laboratory is available. Otherwise baseline will be missing. The measurement from the Run-in Visit will not be used as a baseline value. If more than one measurement was planned for a scheduled time point, for example blood pressure measurements and heart rate, the mean value of the last set of measurements per time point prior to randomization will be used as the baseline value.

Only the data provided by the central laboratory will be used for analysis, values from local laboratories will not be used in the statistical analysis and listed only.

In the event of repeated measurements for Pre-treatment Visits and the Visit 1 (Day 1; baseline), the closest measurement prior to randomization will be used for analysis instead of the scheduled measurements. At all visits post-randomization and unless stated otherwise, only the values at scheduled measurements will be used for analysis.

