6.4.2 Laboratory parameters

The number of subjects with treatment-emergent (until 3 days after any temporary or permanent interruption of study drug) abnormal laboratory values above or below the normal range will be tabulated by the laboratory parameter and treatment group.

Summary statistics including changes to baseline will be calculated by treatment group and visit for all quantitative laboratory parameters, e.g. for hematology, HbA1c, clinical chemistry and urinalysis. Geometric statistics and ratios to baseline will be presented for creatinine and UACR instead of arithmetic statistics with changes from baseline. For eGFR the relative change will be displayed in addition to the absolute change from baseline.

Summary statistics for serum potassium, eGFR and serum creatinine will also be repeated by treatment group and visit separately for each level of the stratification factors.

The following special safety parameters will be further assessed by displaying the number of subjects with treatment-emergent safety events. This will also be performed by visit and by stratification factors. The summaries will be performed for the number of subjects with:

- Absolute value of serum potassium >5.5 mmol/L and >6.0 mmol/L,
- Relative decrease from baseline in eGFR of $\geq 30\%$, $\geq 40\%$, $\geq 50\%$ and $\geq 57\%$
- Absolute value of eGFR <30 mL/min/1.73m².

The percentage of subjects with the respective treatment-emergent events (non-stratified) will be compared between the finerenone and the placebo or active control group by applying separate explorative χ^2 tests with continuity correction. If the expected number of subjects in at least 1 cell of the 2x2 contingency table is less than 5 (see reference 5), Fisher's exact test will be applied instead of the χ^2 test. Estimates and two-sided 95% confidence intervals will be provided for each treatment group and the treatment differences. Clopper Pearson confidence intervals will be calculated for each treatment group, while for treatment differences, due to the computational burden of exact unconditional confidence limits, Wald asymptotic confidence limits will be calculated.

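### The potassium >5.5 and >6.0 mmol/L tables rest on central values alone, which the protocol says can be falsely high; a supportive by-arm table of local values should be added

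*SAP*

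**What the plan says.** **Which values are analysed.** SAP 4.5.3 restricts laboratory analysis to central data and states that "values from local laboratories will not be used in the statistical analysis and will be listed only". The only exception is a subject with no central value for baseline, which cannot affect a post-baseline threshold count. Protocol 10.1 has the same rule: "values from local laboratories will not be used in the statistical analysis and listed only". Protocol 9.7.2.1 is slightly looser: "Only centrally analyzed blood samples will be considered for statistical analysis, unless otherwise specified".

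**What is counted.** SAP 6.4.2 lists "Absolute value of serum potassium >5.5 mmol/L and >6.0 mmol/L" among its special safety parameters, with exploratory tests and confidence limits by arm. SAP 4.5.3 defines the treatment-emergent window as running from the start of study drug to 3 days after any temporary or permanent interruption, unscheduled samples included. Neither section asks for a second, confirming value.

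**What the protocol says about the two laboratories.** Section 9.7.1 reports that "falsely elevated serum potassium values in centrally (but not locally) analyzed samples have been observed in previous studies with finerenone", and attributes this to sample handling and long transport. Local values are described as usually unaffected and available earlier, so "local samples will be taken not only for safety purposes but also for dose adjustments". The same section requires both sources: "During treatment with study drug, all assessments of potassium, including re-tests, will be performed at both local and central laboratories". Table 9-3 has study drug withheld above 5.5 mmol/L, which is also the lower tabulated threshold.

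**The concern.** Hyperkalaemia is named in protocol 3.3 as an important identified risk, and protocol 10.3.4 defines hyperkalaemia and severe hyperkalaemia by these two cut-offs. The plan therefore measures its main safety risk with the source that the protocol itself describes as prone to false elevation. The values that decided whether a subject kept taking drug appear only in listings.

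Two consequences follow. First, a single artefactual central result makes a subject a case even if the local sample was normal and dosing went on. Second, the >5.5 mmol/L count cannot be reconciled with drug withholding, which uses the same cut-off but the other laboratory. Nothing in the protocol or this SAP gives a threshold rate by arm from local values, or shows how often the two laboratories disagree.

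**Working it through.** The documents give no false-elevation rate and no expected hyperkalaemia rate for this trial, so there is no planned figure to reproduce. The text settles which values are counted. The arithmetic below shows only the direction of the effect and a possible size; every rate in it is an assumption.

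**Number of central samples.** From protocol 10.4: 33 months of even recruitment and 44 months in total, so mean follow-up is 44 − 33/2 = 27.5 months. Scheduled central potassium at Months 1, 4, 8, 12, 16, 20 and 24 makes 7, and one up-titration check makes k = 8. This treats the subject as on drug throughout.

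**Model A: the artefact pushes a fixed share of samples over the threshold, whatever the true value.** With per-sample false rate f, independent across samples and unrelated to arm, the share of subjects with at least one false value is F = 1 − (1 − f)^8. The observed risk is p + (1 − p)F, where p is the true risk.

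| Threshold | Assumed true risks | f | F | Observed risks | Ratio | Difference (points) |
|---|---|---|---|---|---|---|
| >5.5 | 16% vs 8% (ratio 2.0, difference 8.0) | 0.5% | 3.93% | 19.30% vs 11.62% | 1.66 | 7.69 |
| >5.5 | same | 1% | 7.73% | 22.49% vs 15.11% | 1.49 | 7.38 |
| >5.5 | same | 2% | 14.92% | 28.54% vs 21.73% | 1.31 | 6.81 |
| >6.0 | 3% vs 1% (ratio 3.0, difference 2.0) | 0.1% | 0.80% | 3.77% vs 1.79% | 2.11 | 1.98 |
| >6.0 | same | 0.5% | 3.93% | 6.81% vs 4.89% | 1.39 | 1.92 |

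Here the difference always shrinks, by the factor (1 − F).

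**Model B: the artefact adds to the true value.** This is closer to what protocol 9.7.1 describes. Assume mean potassium 4.4 mmol/L on placebo and 4.6 on finerenone, between-subject SD 0.30, within-subject SD 0.335, 8 samples, and 5% of samples in both arms raised by 0.5 mmol/L. For a subject with own mean m, one sample stays at or below 5.5 with probability q(m) = 0.95·Φ((5.5 − m)/0.335) + 0.05·Φ((5.0 − m)/0.335). The observed risk is 1 minus the average of q(m)^8 over the distribution of m.

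| | Placebo | Finerenone | Ratio | Difference (points) |
|---|---|---|---|---|
| No artefact | 4.5% | 12.2% | 2.7 | 7.7 |
| With artefact | 7.2% | 16.8% | 2.3 | 9.6 |

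The difference now rises, because the same upward shift carries more samples over a fixed cut-off in the arm whose potassium is already higher.

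**What the two models share.** Both incidences go up and the ratio moves towards 1. They disagree on the sign of the change in the risk difference.

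**The case against.** **Central-only analysis is deliberate.** It is stated consistently in protocol 9.7.2.1, protocol 10.1 and SAP 4.5.3, and it gives one laboratory instead of the local laboratories serving about 900 centres. Local values are only usually free of the artefact. This stands. It is a good reason to keep the central table as the main one and not to pool the two sources; it is no reason to leave local values untabulated.

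**Much of the ground is covered.** Hyperkalaemia hospitalisations and permanent discontinuations (SAP 6.4.1), adverse events, and interruptions with reasons (SAP 6.1.5) are all reported by arm, and the threshold comparisons are exploratory. This also stands, and it limits the weight of the point. These outputs show consequences, however, and none gives a threshold rate.

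**The size is conjecture.** Correct. If false values cluster within subjects, for instance through slow transport from particular sites, the subject-level false rate would be lower than Model A gives.

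**Local sampling does not match the analysis window.** Table 9-1 schedules no local sample at the PD or EOS visit. Its footnote says "Samples to be taken only if the subject is still taking study drug", but protocol 9.7.2.2 requires local potassium until study drug is prematurely discontinued, and 9.7.1 calls for continued monitoring while drug is withheld. A local table therefore needs an explicit window and will miss the last visit.

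**Stronger readings to avoid.** A reader might infer that the artefact makes the excess risk on finerenone look smaller in absolute terms; Model B shows that the absolute excess can grow instead. A reader might also infer that events are hidden. False elevation overcounts cases; it does not remove any.

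**Conclusion.** The point holds as a gap in safety reporting. The threshold tables use the laboratory source that the protocol flags as prone to false elevation, require no confirmation, and have no by-arm local counterpart in the protocol or this SAP. The separate DMC analysis plan was not available, so nothing is said about it.

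The artefact inflates the incidence in both arms. If it is unrelated to treatment, which is reasonable under blinding, it pulls the risk ratio towards 1. The risk difference may move either way. How far any of these move cannot be known from the documents: the ratios of 1.66 to 1.31 (true value 2.0) and 2.11 to 1.39 (true value 3.0) depend on assumed false rates, assumed true rates, and independence between samples. A claim that the distortion is large in this trial would go beyond the evidence.

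No efficacy conclusion is affected. This is a cheap improvement that should be made.

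**What to change.** Keep the central table as the main analysis. Add to SAP 6.4.2, with a matching exception in 4.5.3:

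*Supportive: the number of subjects with any local potassium >5.5 and >6.0 mmol/L within the treatment-emergent window of section 4.5.3 (values more than 3 days into an interruption excluded) will be shown by treatment group. Local and central values from the same visit, drawn within 3 days of each other, will be cross-tabulated above or below each threshold by treatment group. The two sources will not be combined.*

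The cross-tabulation would also show how often the laboratories disagree, which is the quantity now missing.

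**Cost.** Two supportive outputs and no new data, since local potassium is already collected and due to be listed.

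**Limits to state with the tables.** Local methods differ between sites, and no local sample is scheduled at the PD or EOS visit. The addition also departs from the listed-only rule of protocol 10.1, which lacks the qualifier found in 9.7.2.1, so it should be recorded in the SAP as a supportive exception. There is a precedent: SAP 7.3 records the change from exact unconditional to Wald confidence limits for treatment differences in these laboratory comparisons.
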